14. INTERVENTION

a. Digital program

Patients in the digital intervention group will benefit from an 8-week program composed of therapeutic exercise, education and cognitive behavioural therapy (CBT) program provided by SWORD Health. These patients will be referred to SWORD Health by the investigator who identified the candidate. SWORD Health will then assign a physical therapist to each patient. The physical therapist will contact the patient for onboarding and will manage the case.

Patients in this group will performed home-based rehabilitation sessions using SWORD Phoenix[®], under remote monitoring by a physical therapist. Participants will be provided with a tablet computer with a SWORD mobile app installed, along with two inertial motion trackers (each comprised of a gyroscope, an accelerometer and a magnetometer) to be placed on chest, upper arm and wrist, respectively. These trackers enable precise movement quantification, feeding the mobile app, which guides the patient through the session, providing video and audio instructions before each exercise, as well as real-time audio and video biofeedback during the exercise. On the other end, the clinical teams are allowed to remotely monitor results and prescribe/edit exercise sessions through a web-based portal.

The exercise component will follow the protocol outlined in **Annex 2**, which can however be adapted by the physical therapist to the specific needs of the participant. Participants will be asked to start with three 20 min sessions per week, building gradually to three 30 min sessions per week. Participants will not be excluded from the study in case of lower adherence, but will not be included in the per-protocol analysis if they perform less than 21 sessions over the course of 8 weeks.

Participants in this group will be considered as dropouts if they: a) choose to abandon the study;b) do not engage in any exercise session for at least fourteen consecutive days.

The educational component will be delivered automatically through a smartphone app (available for iOS and Android), and will take the form of small educational texts that will be released

periodically to the participant. This component is not mandatory per protocol, but metrics on user engagement will be measured.

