The CBT program will take the form of a self-paced program consisting of written and prerecorded audio materials. An email will be sent weekly by the physical therapist to the participant, during the 8 weeks of the program. Each email will contain an introductory text describing the objectives for that week, as well as a link to that week's audio session and a PDF attachment with self-guided exercises. The CBT component is not mandatory per protocol, but metrics on user engagement will be measured.

b. Conventional PT

Patients in this group will benefit from a 8-week program consisting of two 30 min face-to-face PT sessions per week in an outpatient clinic setting, for a total of 16 sessions. The program will follow the principles outlined in **Annex 3**, which includes commonly used interventions adapted by the physical therapist to the specific needs of the participant.

Participants in this group will be excluded from the per protocol analysis if they complete less than 14 sessions over 8 weeks. Participants in this group will be considered as dropouts if they: a) choose to abandon the study; b) miss four consecutive scheduled PT sessions.

In addition to the face-to-face sessions, PTs will also be communicating with participants in this group through a secure messaging system (Mychart) used at UCSF or, alternatively, through a telephone check-ins (10-15 min calls, up to twice per week).

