16. STATISTICAL ANALYSIS PLAN

To assess differences in clinical and demographic variables of the patients allocated to the two study groups, independent samples t test or Mann–Whitney U test will be used for quantitative variables. For categorical variables, Chi-square test or Fisher's exact test will be used. Outcome analysis will be performed using both an intention to treat analysis and a per-protocol analysis.

The overall impact of the intervention on the primary and secondary outcomes will be assessed considering both the results at the 8-week assessment as well as change from baseline.

Differences between interventions will be evaluated using independent samples t test or Mann-Whitney U test. For non-normally distributed variables, the magnitude of the difference in the medians will be assessed using Hodges-Lehman estimator. Additionally, a repeated measures ANOVA will also be performed, with group as an independent factor and time as a within-subjects factor. When necessary, logarithmic transformation will be performed to obtain normally distributed variables. In all analysis, a significant level of 0.05 will be considered.

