ANNEX 2- DIGITAL THERAPEUTIC EXERCISE PROTOCOL

Should	ler Pain Exercise Protocol	. Phase 1 (week 1)
Goals		Precautions
Recovery of full range of motion (passive and active) Decrease pain and inflammatory signs Gradually increase muscular strength		Do not perform loaded exercises above 70° flexion / abduction
	Intervention	
	Daily Digital Therapis	t Sessions
	Remote session – Assessn	nent/Deploy
Digital Therapist Exercises	Mobility	Strength 1 (External Load – RPE >8)
	Standing Positio)n
Shoulder Flexion	2 sets of 8 reps (alternating)	2 sets of 8 reps (2/5 lbs.) (alternating)
Shoulder Hyperextension	2 sets of 8 reps (alternating)	
Shoulder Abduction	2 sets of 8 reps (alternating)	2 sets of 8 reps (5/7 lbs.) (alternating)
Scapular Plane Elevation	2 sets of 8 reps (alternating)	2 sets of 8 reps (2/5 lbs.) (alternating)
Diagonal 1 Flexion		
Diagonal 2 Flexion	2 sets of 8 reps (alternating)	2 sets of 8 reps (2/5 lbs.) (alternating)
Shoulder External Rotation	2 sets of 8 reps (alternating)	2 sets of 8 reps – Theraband (alternating)
Shoulder Internal Rotation		
Hand to Back	2 sets of 8 reps (alternating)	
Shoulder Horizontal Abduction		2 sets of 8 reps (alternating)
Shoulder Horizontal Adduction		

Shoulder External Rotation in Abduction		3 sets of 8 reps (5/7 lbs.) (alternating)
Shoulder Internal Rotation in Abduction		
Scapulae Retraction with Shoulder Flexion	2 sets of 8 reps (alternating)	
Scapulae Protraction with Shoulder Flexion		
Arm Circles with Shoulder Flexion		
Arm Circles with Shoulder Abduction		2 sets of 8 reps (2/5 lbs.) (alternating)
Chair Press-Up		
Push-Up Against the Wall		
Pendulum		
Estimated Therapy Time	20 min	20 min

Sh	oulder Pain Exercise	e Protocol. Pha	nse 1 (weeks	2 to 4)
Goals			Precautions	
Recovery of full range of motion (passive and active) Decrease pain and inflammatory signs Gradually increase muscular strength		Do not per	form loaded exercises above 70° flexion / abduction	
]	Intervention		
		ital Therapist S		
	4-Week	Remote Assess		1
Digital Therapist Exercises	Mobility	Strength 1 Load – F		Strength 2 (External Load – RPE >8)
	Star	nding Position		
Forearm Supination	2 sets of 10 reps (alternating)			
Elbow Flexion		2 sets of (alterna		
Shoulder Flexion	2 sets of 10 reps (alternating)	2 sets of 10 lbs.) (alte		
Shoulder Hyperextension	2 sets of 10 reps (alternating)			2 sets of 10 reps – Theraband (alternating)
Shoulder Abduction	2 sets of 10 reps (alternating)	2 sets of 10 lbs.) (alte		

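### The per-protocol comparison is selected by adherence after randomisation, is tested without covariates and is not ranked below ITT, so it is biased if the link between patient characteristics and completion differs by arm.

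*Combined protocol and SAP*

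**What the plan says.** Section 16 (Statistical Analysis Plan) orders two analysis sets: "Outcome analysis will be performed using both an intention to treat analysis and a per-protocol analysis". For the group contrast it says: "Differences between interventions will be evaluated using independent samples t test or Mann-Whitney U test". Outcomes are examined both as the 8-week result and as change from baseline, and a repeated measures ANOVA with group and time is added. The 0.05 level applies throughout. No covariate, weighting or sensitivity analysis is given for the per-protocol set, and the section does not say that ITT takes precedence.

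Section 14 (Intervention) defines who stays in the per-protocol set:

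- **Digital arm:** patients "will not be included in the per-protocol analysis if they perform less than 21 sessions over the course of 8 weeks". The prescription starts at three 20-minute sessions a week, "building gradually to three 30 min sessions per week".
- **Conventional arm:** "Participants in this group will be excluded from the per protocol analysis if they complete less than 14 sessions over 8 weeks". The prescription is "two 30 min face-to-face PT sessions per week in an outpatient clinic setting, for a total of 16 sessions".

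The study hypothesis (section 6) is that the digital program does at least as well as conventional PT.

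**The concern.** Both rules act on what patients do after allocation. The act differs by arm: exercising alone at home in one, attending a clinic in the other. It is plausible, though the documents do not say so, that different kinds of patient complete each program. The two retained groups would then differ in prognosis, and a two-sample test would read that difference as a treatment effect. Such a bias can create a difference or hide one.

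What is at stake is the weight given to the result. The hypothesis is of the at-least-as-good kind and has no margin. A per-protocol result showing no difference, or one favouring the digital arm, could be offered as support, and nothing in section 16 makes it subordinate to ITT.

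**Working it through.** **1. The hurdles.**
- Digital: 3 sessions × 8 weeks = 24, and 21/24 = 87.5%.
- Conventional: 2 × 8 = 16, and 14/16 = 87.5%.

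Relative to section 14 the hurdles are equally strict. The Annex 2 tables, however, label the digital sessions as daily. Read literally that is 7 × 8 = 56 sessions, and 21/56 = 37.5%. Section 14 and Annex 2 must be reconciled.

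**2. How many might be kept.** The plan gives no expected adherence. If each session is completed independently with probability p, the share passing is P(X ≥ 21 | 24, p) or P(X ≥ 14 | 16, p):

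| p (assumed) | Digital | Conventional |
|---|---|---|
| 0.80 | 26% | 35% |
| 0.85 | 50% | 56% |
| 0.90 | 79% | 79% |

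Selection could be heavy or light; about 60% kept is used below.

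**3. Selection on baseline severity.** Inputs from section 9: 40 per arm, SD 19, and the 11.2-point difference for scale. Assumed: no true effect, baseline to 8-week correlation r = 0.5, and logistic completion centred at 60% with odds ratio 2 per SD of baseline QuickDASH. If the kept patients in an arm have a mean baseline shifted by d SD, then

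- bias of the 8-week score = 19 × r × d
- bias of change from baseline = −19 × (1 − r) × d

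Results of t tests over at least 6,000 simulated trials per scenario (signs depend only on which arm is labelled first):

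| Completion depends on severity | 8-week score: bias, type I error | Change: bias, type I error | Adjusted for baseline: bias, type I error |
|---|---|---|---|
| In one arm only | about −2.5, 7-8% | about +2.5, 7-8% | below 0.1, about 5% |
| In opposite directions | about −4.8, about 14% | about +4.9, about 14% | below 0.1, about 5% |
| Same way in both arms | about 0, about 5% | about 0, about 5% | about 0, about 5% |

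Check: 2.5 / (19 × 0.5) gives d of about 0.26 SD. The opposite-direction case doubles it: 2 × 0.26 × 9.5 = 4.9. On the scale of the planned difference, 4.8/11.2 = 43%. The two outcome scales err by equal amounts because r = 1 − r at r = 0.5; at other correlations the sizes differ but the signs remain opposite.

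**4. Selection on what baseline does not explain.** Same set-up, but completion now depends on the part of the 8-week score unrelated to baseline. The expected bias is 19 × √(1 − 0.5²) × 0.26 = 4.3.
- One arm only: bias about −4.3 both unadjusted and adjusted; type I error about 12% unadjusted, 13-15% adjusted.
- Opposite directions: bias about −8.5 both ways; type I error about 34% unadjusted, about 44% adjusted.

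The near-zero adjusted bias in step 3 therefore follows from making the driver of completion the same variable as the covariate. It is not a general result.

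**5. A second selection model.** Let latent adherence correlate ρ with outcome and let a share q pass. Bias = 19 × [ρ_D λ(q_D) − ρ_C λ(q_C)], with λ(q) = φ(z(1−q))/q, so λ(0.6) = 0.644, λ(0.7) = 0.497 and λ(0.8) = 0.350.
- Equal q, equal ρ: bias 0, type I error 5%.
- q of 60% and 80%, ρ = 0.2 to 0.5 in both arms: 19 × ρ × 0.294 = 1.1 to 2.8 points; type I error 5.6% to 9.0%.
- q = 70% in both arms, ρ = 0.5 in one and 0 in the other: 19 × 0.5 × 0.497 = 4.7 points; type I error 16%.

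Both models agree: bias needs a difference between arms, either in the share kept or in the link between completion and outcome.

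**The case against.** The strongest reply has four parts.

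- **The hurdles are comparable.** A reader might infer from 21 against 14 that unequal thresholds are themselves the fault. The documents do not support that: both are 87.5% of the section 14 prescription. This part stands.
- **The bias is not established.** No passage says what drives attendance in either arm. The 14% error rate needs selection of opposite sign, for which the documents offer no evidence. With an odds ratio of 1.3 in one arm only, the bias is about 1 point and type I error about 5%. This stands too: the figures are illustrations, not forecasts.
- **The plan already uses baseline and ITT.** Change from baseline and the ANOVA do bring in the baseline score, and ITT is planned and listed first. But the change score does not remove the bias; under selection on severity it reverses it. The two planned scales could then disagree, with no rule for choosing between them. Listing ITT first is not the same as giving it precedence.
- **Adjustment may buy little.** A reader might infer that a covariate model cures the problem. It does so only for measured baseline variables. Motivation is not among the baseline items in section 15, and step 4 shows no gain when completion depends on something unmeasured. This stands and belongs in the SAP as a limitation.

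None of this makes an unadjusted test on an adherence-selected set, unranked against ITT, a sound plan.

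**Conclusion.** The point holds in a limited form. The per-protocol comparison is conditioned on adherence after randomisation, is tested without covariates at 0.05, and is not placed below ITT. It is biased if the share completing, or the link between patient characteristics and completion, differs by arm, and unbiased if both are the same.

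Neither the existence nor the size of bias can be fixed from the documents. Under the stated assumptions (odds ratio 2 per SD of severity, r = 0.5, about 60% of 40 per arm kept, SD 19), the 8-week comparison is off by about 2.5 points with one-arm dependence and about 4.8 points with opposite dependence. Type I error is 7-8% and about 14%, and the change score is biased the other way. Only the t test was simulated, not the Mann-Whitney or the ANOVA.

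The documents do not support reading this as proof that the per-protocol result will mislead, or that the trial's conclusion rests on it.

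**What to change.** In section 16:

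1. Name ITT as the primary analysis and per-protocol as supportive, and state that no conclusion rests on the per-protocol set alone.
2. Replace the per-protocol two-sample test with a linear model of the 8-week score on arm and baseline score. Baseline pain, age and working status may be added if fixed in advance; section 15 already collects them. Modelling change instead, with the same covariates, gives the same arm estimate, so the conflict between the two scales disappears.
3. Report the number kept in each arm.
4. State that selection on motivation or early response is not corrected.

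Separately, reconcile section 14 with the Annex 2 labelling, so that the share of prescribed sessions behind the digital hurdle is clear.

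Arm-specific adherence weights are not an interchangeable alternative. They target all randomised patients rather than completers. They would also be unstable here: with 60% to 79% kept, each arm has only about 40 × 0.40 = 16 down to 40 × 0.21 = 8 non-completers.

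The cost is SAP wording and a short change to the analysis code, with no new data or visits. The model uses one degree of freedom for the baseline score and a few more with the optional covariates, from about 2 × 40 × 0.6 = 48 patients if 60% are kept. If completion turns on unmeasured factors, the adjusted result is as biased as the unadjusted one and somewhat more likely to cross 0.05, which is why the ranking in item 1 matters more than the model in item 2.

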8. STUDY OUTCOMES

8.1 Primary Outcome

Impact on physical function and symptoms measured through the shortened Disabilities of the Arm, Shoulder and Hand questionnaire (QuickDASH) between baseline and 8 weeks.

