9. SAMPLE SIZE ESTIMATION

Sample size estimation calculations were performed taking into consideration the primary outcome measure – the QuickDASH. In a sample of 57 patients with shoulder tendon disorders treated with SWORD Health's medical device in the context of work-related conditions, the mean and standard deviation of the QuickDASH scale at baseline was of 59 and 19 points respectively. A Minimal Detectable Difference (MDD) of 11.2 points was considered, based on the psychometric properties of the scale.⁵⁶ Considering a power of 80%, a two-sided 0.05 significance level and a 10% dropout rate, 80 (40+40) patients would be necessary to detect a 11.2 points difference between the two groups.

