Patients will be randomly allocated to one of two groups, using random permuted blocks of 6. After eConsent collection, the investigator will enter the EDC portal and proceed with randomisation (also built into the EDC). Following randomisation, the investigator will contact the person responsible for the rehabilitation program in each group to allocate the participant to the respective study arm. Blinding of investigators and patients regarding allocation arm will not be possible, given the nature of the intervention. Analysis of study results will be performed by an independent statistician at UCSF.

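### No single primary QuickDASH analysis is named (outcome form, test, analysis set) and baseline is never a covariate; fix one, preferably week-8 ANCOVA in all randomised participants

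*Combined protocol and SAP*

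**What the plan says.** Section 8.1 makes QuickDASH the primary outcome, measured "between baseline and 8 weeks". Section 16 then assesses primary and secondary outcomes "considering both the results at the 8-week assessment as well as change from baseline". Groups are compared by independent samples t test or Mann-Whitney test, and a further model follows: "Additionally, a repeated measures ANOVA will also be performed, with group as an independent factor and time as a within-subjects factor". On analysis sets: "Outcome analysis will be performed using both an intention to treat analysis and a per-protocol analysis". On the error rate: "In all analysis, a significant level of 0.05 will be considered". On distribution: "When necessary, logarithmic transformation will be performed to obtain normally distributed variables".

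No outcome form, test or set is ranked above the others. Section 14 says which participants leave the per-protocol set (fewer than 21 sessions in the digital arm, fewer than 14 in the conventional arm) but not whether that set or the intention-to-treat set decides. Intention to treat is not defined. No covariate appears anywhere in the plan.

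**The concern.** The clearest gaps are week-8 value versus change, and intention to treat versus per-protocol. The ANOVA reads as supplementary. Section 8.1 leans towards change, but section 9 sizes the trial on a single-visit SD, which fits a week-8 value, and section 16 applies both forms.

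The two forms are different tests and can give different verdicts on the same data. Section 13 states: "Blinding of investigators and patients regarding allocation arm will not be possible, given the nature of the intervention". The choice should therefore be in writing before anyone sees results by arm.

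Neither t test makes good use of baseline. The week-8 test ignores it; the change test subtracts it with a fixed weight of 1, whatever the correlation between visits. Precision is lost that the trial could have at almost no cost. It matters whether the result is read as a difference or against the section 6 hypothesis that the digital arm does no worse, because both readings depend on the width of the interval.

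**Working it through.** **Inputs from the documents.** Section 9: "the mean and standard deviation of the QuickDASH scale at baseline was of 59 and 19 points respectively"; difference 11.2; two-sided 0.05; 80% power; 10% dropout; 40 per arm. Evaluable per arm: 40 × 0.9 = 36.

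**Assumed, not in the documents.** Baseline to week-8 correlation r = 0.3, 0.5, 0.7; week-8 SD s8 = 14, 19, 22; normal data.

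**The plan's own figure.** By the normal approximation, n per arm = 2 × (1.960 + 0.842)² × 19² / 11.2² = 45.2, so 46. After dropout this is 52 per arm, total 104, not 80. With one-sided 0.05 the formula gives 35.6, so 36, then 40 per arm and a total of 80. This is a separate issue, set aside here; the checks below keep 36 per arm and two-sided 0.05.

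**SD that each analysis works with.**
- Week-8 value: s8
- Change: √(19² + s8² − 2 × r × 19 × s8)
- ANCOVA: s8 × √(1 − r²)

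At s8 = 19 and r = 0.5, change has SD √(361 + 361 − 361) = 19.0 and ANCOVA has 19 × √0.75 = 16.5.

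**Which t test is better?** Change is noisier than the week-8 value when r < 19 / (2 × s8). The threshold is 0.68, 0.50 or 0.43 for s8 = 14, 19 or 22. Plausible correlations lie on both sides of it.

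**Power for a difference of 11.2** (noncentral t; 70 df, 69 for ANCOVA; triplets are r = 0.3/0.5/0.7):

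| s8 | Week-8 value | Change | ANCOVA | Gain over better t test (points) |
|---|---|---|---|---|
| 14 | 92% | 65/78/93% | 94/97/99.7% | 2.2/5.4/6.5 |
| 19 | 69% | 55/69/89% | 73/81/93% | 4/12/4 |
| 22 | 57% | 48.5/62/83% | 61/69/85% | 4.0/7.0/1.8 |

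The group-by-time test at SD 19 (noncentral F, 2 and 140 df) reaches 45/59/82% if the week-4 effect is half of 11.2, and 57/73/92% if it is zero or full. ANCOVA exceeds both.

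**95% CI half-width at s8 = 19** (t × SD × √(2/36)): value 8.9; change 10.6/8.9/6.9; ANCOVA 8.5/7.7/6.4.

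**How often the two t tests disagree at p < 0.05** (simulation, 40,000 trials per cell). True difference 11.2: 31/29/29% at s8 = 19, and 14-34% across s8 = 14 to 22. No difference: 7-10%.

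**Illustration only.** Suppose any one significant result could support the conclusion, a rule the plan neither states nor excludes. With no true difference and s8 = 19, value or change is significant in 8.8-9.3% of trials, about half of them favouring the digital arm (4.3-4.8%, against 2.5% for one test). Allowing either analysis set as well gives 11-15%, and ANCOVA in either set gives 6-8%. The figures involving the per-protocol set treat it as a random 61-89% of each arm. In the plan it is defined by adherence, so they are rough.

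**The case against.** The strongest reply is that two points are joined here and only one is a defect. An unadjusted t test in a randomised trial is valid; in simulation each held its 5% level (0.049-0.051). Naming any one form, test and set would remove the ambiguity. ANCOVA is then an efficiency gain of about 2 to 12 points, and the 12 occurs only where the two t tests tie. This is fair as to kind: the missing primary analysis is the defect, and ANCOVA is the better way to fill it. It was at least as powerful as the better t test in all nine cells and needs no guess at r or s8.

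Section 13 also assigns the analysis to an independent statistician. That reduces the scope for interested choice, but the plan gives the statistician no rule on which result counts and does not say that this person is blinded to arm.

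The 3-in-10 disagreement does assume a true difference of 11.2; the rate under no difference is 7-10%. The any-one-significant figures deserve little weight and the conclusion does not rest on them.

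Two further points stand as additions. ANCOVA drops anyone without a week-8 score, so an all-randomised analysis needs a missing-data rule. And section 15 places the window for the final questionnaire at the start of week 4 under its 8-week heading, which must be reconciled with a week-8 outcome.

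**Conclusion.** The concern holds. Section 16 leaves the primary QuickDASH analysis open on form, test and set, and sections 8.1, 9 and 14 do not close it. At the planning SD and a true difference of 11.2, the two t tests would disagree in about 3 trials in 10. Using baseline as a covariate raises power by about 2 to 12 points over the better t test across the range examined and narrows the interval. With baseline in the model, the treatment estimate is the same whether the outcome is the week-8 value or change, so the question of form disappears.

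The sizes rest on 36 evaluable per arm, normal data, and assumed values for r and the week-8 SD. The finding that nothing is named rests on no assumption. This should be corrected; it does not invalidate the design.

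**What to change.** Before any outcome data by arm are reviewed, state one primary analysis in section 16: week-8 QuickDASH by ANCOVA with treatment and baseline QuickDASH, in all randomised participants, reported as an adjusted mean difference with 95% CI. Label the unadjusted week-8 and change tests, the ANOVA and the per-protocol analysis as supportive. Name the set as well as the test. Exclude change scores from the log-transformation rule, since they can be zero or negative. Add a rule for missing week-8 scores.

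Cost: SAP wording and a covariate already collected at baseline, with no new visits or instruments. Section 15 also needs rewording so that its exclusion of participants with unfilled forms does not remove randomised people from the intention-to-treat set. That sentence sits under the baseline heading, so its reach to week 8 is an inference; if it does reach week 8, forms must also be requested from those now excluded.

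The missing margin for the section 6 hypothesis and the shortfall in N = 80 are separate issues. If a margin is set, decide the role of the per-protocol set at the same time.
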